APPENDIX 1 TFLs Shells

Subjects with more than one TEAE will be counted once in the maximum severity or strongest relationship category.

Path to the program code, date and time of output/ Datasets used/ Referenced Data Listings

**MC2-01-C6_STATISTICAL ANALYSIS PLAN_Final 3.0_07 September 2020**
APPENDIX 1 TFLs ShellsMC2 Therapeutics
MC2-01-C6**Table 14.3.1.2.1 Incidence of Treatment-emergent Adverse Events**
Safety population
Page X of X

| System Organ Class (SOC) Preferred Term (PT) | Total (N = XX) n (%) / E |
|---|--------------------------------|
| Overall | XX (XX.X) / XX |
| System Organ Class 1 | XX (XX.X) / XX |
| Preferred Term 1 | XX (XX.X) / XX |
| Preferred Term 2 | XX (XX.X) / XX |
| ... | ... |
| System Organ Class 2 | XX (XX.X) / XX |
| Preferred Term 1 | XX (XX.X) / XX |
| Preferred Term 2 | XX (XX.X) / XX |
| ... | ... |

AE=Adverse Event; MedDRA=Medical Dictionary for Regulatory Activities; TEAE=Treatment-Emergent Adverse Event.

N: the number of subjects in the Safety population.

n: the number of subjects with at least one TEAE within a specific category. Percentages are calculated as $(100 \times n/N)$.

E: total number of TEAEs reported within a specific category.

Adverse events are coded by MedDRA version XX.X.

Path to the program code, date and time of output/ Datasets used/ Referenced Data Listings

Programming note:

System organ classes (SOC) and preferred terms (PT) within each SOC should be sorted in descending order of n (%).

Each subject is counted only once per preferred term (PT) and once per system organ class (SOC).

MC2-01-C6_STATISTICAL ANALYSIS PLAN_Final 3.0_07 September 2020
APPENDIX 1 TFLs Shells

Similar to table 14.3.1.2.1, the following tables will be constructed (with the corresponding corrections of underlined fragments in the note):

Table 14.3.1.2.2 Incidence of Treatment-emergent Adverse Events up to Week 4
Table 14.3.1.3.1 Incidence of Treatment-emergent Adverse Events Related to the Study Drug
Table 14.3.1.3.2 Incidence of Treatment-emergent Adverse Events Related to the Study Drug up to Week 4
Table 14.3.1.4.1 Incidence of Serious Treatment-emergent Adverse Events
Table 14.3.1.4.2 Incidence of Serious Treatment-emergent Adverse Events up to Week 4
Table 14.3.1.5.1 Incidence of Serious Treatment-emergent Adverse Events Related to the Study Drug
Table 14.3.1.5.2 Incidence of Serious Treatment-emergent Adverse Events Related to the Study Drug up to Week 4

MC2-01-C6_STATISTICAL ANALYSIS PLAN_Final 3.0_07 September 2020
APPENDIX 1 TFLs ShellsMC2 Therapeutics
MC2-01-C6Table 14.3.1.6.1 Incidence of Treatment-emergent Adverse Events by Maximum Severity
Safety population
Page X of X

| System Organ Class (SOC) Preferred Term (PT) | Severity | Total (N = XX) n (%) / E |
|---|----------------------------|--|
| Overall | Mild Moderate Severe | XX (XX.X) / XX XX (XX.X) / XX XX (XX.X) / XX |
| System Organ Class 1 | Mild Moderate Severe | XX (XX.X) / XX XX (XX.X) / XX XX (XX.X) / XX |
| Preferred Term 1 | Mild Moderate Severe | XX (XX.X) / XX XX (XX.X) / XX XX (XX.X) / XX |
| Preferred Term 2 | Mild Moderate Severe | XX (XX.X) / XX XX (XX.X) / XX XX (XX.X) / XX |
| ... | ... | ... |
| System Organ Class 2 | Mild Moderate Severe | XX (XX.X) / XX XX (XX.X) / XX XX (XX.X) / XX |
| ... | ... | ... |

AE=Adverse Event; MedDRA=Medical Dictionary for Regulatory Activities; TEAE=Treatment-Emergent Adverse Event.

N: the number of subjects in the Safety population.

n: the number of subjects with at least one TEAE within a specific category. Percentages are calculated as $(100 \times n/N)$.

E: total number of TEAEs reported with appropriate severity.

For 'Overall' and for each SOC and SOC/PT, each subject is counted once in the category of the maximum severity.

For 'Overall', the number of all reported TEAEs are presented; for each SOC and SOC/PT, the number of TEAEs of maximum severity is given.

If the severity is missing for a TEAE, then 'Severe' category is assigned.

AEs are coded using MedDRA version XX.X.

Path to the program code, date and time of output/ Datasets used/ Referenced Data Listings

MC2-01-C6_STATISTICAL ANALYSIS PLAN_Final 3.0_07 September 2020

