**MC2-01-C6_STATISTICAL ANALYSIS PLAN_Final 3.0_07 September 2020**

severity (mild, moderate, or severe), and by relationship to trial product (none, possible, probable, or definite). An AE is treatment-emergent if its date of onset is on or after the date of the first application of the IP.

Only treatment emergent AEs will be summarized. In the listings, however, all occurrences of the AEs will be presented.

Number (percentage) of subjects and number of AEs will be presented for the Safety population in the following tables:

- All treatment-emergent AE / SAE;
- Treatment-emergent AE / SAE related to the study drug (relationship to trial product assessed by the investigator as possible, probable, or definite including those events where assessment is missing);
- TEAE by maximum severity;
- TEAE by closest relationship to study drug;
- TEAE related to study drug by maximum severity;
- TEAE related to cosyntropin;
- TEAE related to study procedures;
- TEAE leading to the permanent discontinuation of study drug (Action taken with IP=“Drug withdrawn”);
- TEAE leading to withdrawal (Did subject withdraw due to this AE? = “Yes”);
- TEAE leading to death (Outcome = “Death”);
- Non-serious TEAEs that occurred at a frequency of $\geq 5\%$ (if no events occurred at the 5% threshold all non-serious TEAEs will be tabulated).

This set of tables will be repeated for the adverse events occurring up to Visit 3 / Week 4. Treatment-emergent adverse events with start dates on or prior to Visit 3 / Week 4 date will be summarized separately. If subject discontinued from the study prior to Visit 3 / Week 4 his/her adverse events will also be included in these summaries. If subject missed Visit 3 / Week 4 the planned date of visit (study day) will be used to subset the events occurring up to Week 4.

Tables of TEAEs by maximum severity (closest relationship to study drug) will be prepared using the following rules: each SOC / PT category will include only the AEs with the worst severity (closest relationship) for each subject. In the Overall category, all AEs of the subjects will be presented. Each subject will be counted only once with the worst severity (closest relationship) in each SOC and each PT level as well as in the Overall level.

In case if severity or relationship to study drug is missing, the worst case value will be assumed and used in the summary.

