APPENDIX 1 TFLs ShellsMC2 Therapeutics
MC2-01-C6Table 14.3.1.7.1 Incidence of Treatment-Emergent Adverse Events by Closest Relationship
Safety population
Page X of X

| System Organ Class (SOC) Preferred Term (PT) | Relationship | Total (N = XX) n (%) / E |
|---|--------------------|--------------------------------|
| Overall | Not related | XX (XX.X) / XX |
| | Possibly related | XX (XX.X) / XX |
| | Probably related | XX (XX.X) / XX |
| | Definitely related | XX (XX.X) / XX |
| System Organ Class 1 | Not related | XX (XX.X) / XX |
| | Possibly related | XX (XX.X) / XX |
| | Probably related | XX (XX.X) / XX |
| | Definitely related | XX (XX.X) / XX |
| Preferred Term 1 | Not related | XX (XX.X) / XX |
| | Possibly related | XX (XX.X) / XX |
| | Probably related | XX (XX.X) / XX |
| | Definitely related | XX (XX.X) / XX |
| Preferred Term 2 | Not related | XX (XX.X) / XX |
| | Possibly related | XX (XX.X) / XX |
| | Probably related | XX (XX.X) / XX |
| | Definitely related | XX (XX.X) / XX |
| ... | ... | ... |
| System Organ Class 2 | Not related | XX (XX.X) / XX |
| | Possibly related | XX (XX.X) / XX |
| | Probably related | XX (XX.X) / XX |
| | Definitely related | XX (XX.X) / XX |
| ... | ... | ... |

AE=Adverse Event; MedDRA=Medical Dictionary for Regulatory Activities; TEAE=Treatment-Emergent Adverse Event.

N: the number of subjects in the Safety population.

n: the number of subjects with at least one TEAE within a specific category. Percentages are calculated as $(100 \times n/N)$.

E: total number of TEAEs reported with given category of relationship to study drug.

For 'Overall' and for each SOC and SOC/PT, each subject is counted once in the category of the closest relationship.

For 'Overall', the number of all reported TEAEs are presented; for each SOC and SOC/PT, the number of TEAEs of closest relationship is given.

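### In the adverse event tables by severity and by relationship, the event count E follows one rule in the Overall rows and another in the SOC and PT rows, against its own definition

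*SAP*

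**What the plan says.** SAP 9.2 sets the counting rules for the tables by maximum severity and by closest relationship. At the lower levels, "each SOC / PT category will include only the AEs with the worst severity (closest relationship) for each subject". For the top level the rule differs: "In the Overall category, all AEs of the subjects will be presented".

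The shells in SAP Appendix 1 repeat the split. Table 14.3.1.6.1 states: "For 'Overall', the number of all reported TEAEs are presented; for each SOC and SOC/PT, the number of TEAEs of maximum severity is given". Table 14.3.1.7.1 states: "For 'Overall', the number of all reported TEAEs are presented; for each SOC and SOC/PT, the number of TEAEs of closest relationship is given". The versions up to Week 4 (14.3.1.6.2 and 14.3.1.7.2) are built on the same shells, so four outputs are concerned.

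Both shells also define E. For severity: "E: total number of TEAEs reported with appropriate severity". For relationship: "E: total number of TEAEs reported with given category of relationship to study drug". Neither definition limits E to a subject's worst event.

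Subjects are counted one way throughout: "For 'Overall' and for each SOC and SOC/PT, each subject is counted once in the category of the maximum severity". The relationship shell has the parallel rule.

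**The concern.** Counting subjects once, at their worst grade, is normal practice and is not in question. The difficulty lies in E. A reader who takes E from its footnote expects each PT row to give the number of events reported at that severity or relationship. Under the rule beside it, the row gives only the events at each subject's worst grade. E in the Overall rows does match the definition, so one column carries two meanings.

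Three things follow when a subject has events of different grade within a PT or SOC:

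- PT and SOC rows can understate E against its definition.
- SOC rows do not sum to Overall, and PT rows do not sum to their SOC.
- The PT totals do not agree with Table 14.3.1.2.1, which counts every TEAE by SOC and PT: "E: total number of TEAEs reported within a specific category".

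What is at stake is the readability and internal agreement of four safety tables. The protocol synopsis names adverse event incidence and severity as a safety criterion. The interim analysis follows completion by 7 treated subjects (SAP 6.1), and its report goes to FDA (SAP 6.4). With so few subjects, one subject's events can visibly shift the column.

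**Working it through.** The shells hold placeholders only, so there is no planned figure to reproduce. The check applies the stated rules to small assumed data sets. These are illustrations and not trial data.

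**Rules applied**

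- n in a row = subjects whose worst grade within that level is the row's grade (SAP 9.2 and both shells).
- E in an Overall row = all TEAEs of that grade. This reads the Overall rule together with the definition of E.
- E in a SOC or PT row = TEAEs of that grade belonging to subjects for whom it is the worst grade within that SOC or PT.

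**Example 1: one subject, one PT, 5 mild and 1 moderate TEAEs**

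- PT rows: Mild E = 0, Moderate E = 1, total 0 + 1 = 1.
- Overall rows: Mild E = 5, Moderate E = 1, total 5 + 1 = 6.
- By its definition, the PT Mild row should show E = 5.
- The Overall Mild row shows n = 0 with E = 5, because n uses the worst grade and E uses every event.

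**Example 2: one subject, one PT, 3 possibly and 1 probably related TEAEs**

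- PT rows: Possibly E = 0, Probably E = 1, total 1 of 4.
- Overall rows: 3 + 1 = 4.

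**Example 3: two subjects, six TEAEs**

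Subject 1 has PT1 (SOC1) mild, mild and severe, and PT2 (SOC1) mild. Subject 2 has PT1 (SOC1) mild and PT3 (SOC2) moderate.

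| Row | Mild n / E | Moderate n / E | Severe n / E | Sum of E, SAP rule | Sum of E, every event by own grade |
|---|---|---|---|---|---|
| Overall | 0 / 4 | 1 / 1 | 1 / 1 | 6 | 6 |
| SOC1 | 1 / 1 | 0 / 0 | 1 / 1 | 2 | 5 |
| PT1 | 1 / 1 | 0 / 0 | 1 / 1 | 2 | 4 |
| PT2 | 1 / 1 | 0 / 0 | 0 / 0 | 1 | 1 |
| SOC2 | 0 / 0 | 1 / 1 | 0 / 0 | 1 | 1 |
| PT3 | 0 / 0 | 1 / 1 | 0 / 0 | 1 | 1 |

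- SOC rows against Overall: 2 + 1 = 3 under the SAP rule, against 6. Under one all-events rule, 5 + 1 = 6.
- PT rows against SOC1: 2 + 1 = 3 under the SAP rule, against 2. Under one all-events rule, 4 + 1 = 5.
- PT1 Mild shows E = 1, although three mild PT1 events were reported.
- Three of subject 1's mild events are missing from the SOC1 row. Two of them, the repeat PT1 events, are missing from every SOC and PT row. The third is the single PT2 event, so the effect is not confined to repeats of one term.
- Table 14.3.1.2.1 would show E = 4 for PT1, where Table 14.3.1.6.1 shows 2.

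If no subject has events of different grade within a PT or SOC, both rules give the same counts and the rows agree with the definition.

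**The case against.** The rule is deliberate, disclosed, and the same in SAP 9.2 and both shells. Protocol 8.8.3 asks for incidence, with each subject contributing once. It does not ask for event counts, so E is supplementary. In the SOC and PT rows the rule keeps n and E on the same worst-grade events, which is a defensible presentation. For severity, the word describing the grade in the footnote could be stretched to mean the worst one. All of this stands as a limit on the importance of the point. It does not remove the mismatch, which is plain in the relationship footnote and is the natural reading of the severity footnote.

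A reader might infer more than the documents support:

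- **That events disappear from the report.** They do not. Each one is in the Overall rows, in Table 14.3.1.2.1, and in Listing 16.2.7.1 with its own severity and relationship.
- **That related events go uncounted within SOC and PT.** Table 14.3.1.3.1 and its Week 4 version count all related TEAEs (possible, probable or definite) by SOC and PT. In Example 2 that PT row shows all 4. Only the direct split by category is missing.
- **That the split can never be recovered.** If one subject accounts for the PT, it sometimes can. In Example 1, 6 events in Table 14.3.1.2.1 less 1 at the moderate maximum leaves 5, which must be mild. If the maximum is severe, the remainder could be mild or moderate, and the listing may be needed.
- **That repeated local reactions make the problem likely here.** No passage says so. Protocol 2.3 describes the reactions in earlier adolescent trials as few and mild. Local skin reactions have their own graded assessment (Protocol 7.9.3, SAP 9.5). Protocol 7.10.3 grades an event at its maximum intensity, so fluctuation within one event does not create several records.

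**Conclusion.** The point holds as a low-impact reporting error in four safety tables. E is counted by two rules in one column, and its SOC and PT values contradict its footnote definition whenever a subject has events of differing grade within a PT or SOC. The only quantity affected is the event count by grade within SOC and PT. n (%) and the primary HPA and calcium analyses are untouched, and no safety data are lost.

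The size depends on the data. It is zero without mixed grades, and in the assumed examples 1 of 6, 1 of 4 and, for the SOC rows, 3 of 6 events are shown. The conclusion assumes that E in the Overall rows is split by each event's own grade and that the E footnotes refer to the grade of the row. How often mixed grades will occur in this trial cannot be judged from the documents.

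**What to change.** Use one rule for E at every level in SAP 9.2 and in Tables 14.3.1.6.1, 14.3.1.6.2, 14.3.1.7.1 and 14.3.1.7.2. Either option resolves the contradiction.

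1. **Count every event by its own grade.** Keep n (%) by worst severity or closest relationship. Count E under each TEAE's own severity or relationship at Overall, SOC and PT, and delete the sentences that set a separate rule. Add a footnote such as: *n counts each subject once, at the worst grade within the level; E counts each TEAE under its own grade, so a row may show n = 0 with E > 0.* E then adds up across levels and agrees with Table 14.3.1.2.1. The drawback is that n and E in a row describe different sets of events. In Example 1, n = 0 with E = 5 would appear at SOC and PT as well as Overall, so the footnote is essential.
2. **Drop E from these four tables** and show n (%) only, as Table 14.3.1.1 already does for maximum severity and strongest relationship. The drawback is that these tables then carry no event count.

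Either way the cost is SAP and shell wording plus a small program change, with no new data. SAP Section 2 allows revision before the database lock for the interim analysis. After that, the change would be a deviation explained in the clinical study report.

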APPENDIX 1 TFLs Shells

Programming note:

System organ classes (SOC) and preferred terms (PT) within each SOC should be sorted in descending order of n (%).

Similar to table 14.3.1.6.1, the following tables will be constructed:

Table 14.3.1.6.2 Incidence of Treatment-emergent Adverse Events up to Week 4 by Maximum Severity

MC2-01-C6_STATISTICAL ANALYSIS PLAN_Final 3.0_07 September 2020
APPENDIX 1 TFLs ShellsMC2 Therapeutics
MC2-01-C6Table 14.3.1.7.1 Incidence of Treatment-Emergent Adverse Events by Closest Relationship
Safety population
Page X of X

| System Organ Class (SOC) Preferred Term (PT) | Relationship | Total (N = XX) n (%) / E |
|---|--------------------|--------------------------------|
| Overall | Not related | XX (XX.X) / XX |
| | Possibly related | XX (XX.X) / XX |
| | Probably related | XX (XX.X) / XX |
| | Definitely related | XX (XX.X) / XX |
| System Organ Class 1 | Not related | XX (XX.X) / XX |
| | Possibly related | XX (XX.X) / XX |
| | Probably related | XX (XX.X) / XX |
| | Definitely related | XX (XX.X) / XX |
| Preferred Term 1 | Not related | XX (XX.X) / XX |
| | Possibly related | XX (XX.X) / XX |
| | Probably related | XX (XX.X) / XX |
| | Definitely related | XX (XX.X) / XX |
| Preferred Term 2 | Not related | XX (XX.X) / XX |
| | Possibly related | XX (XX.X) / XX |
| | Probably related | XX (XX.X) / XX |
| | Definitely related | XX (XX.X) / XX |
| ... | ... | ... |
| System Organ Class 2 | Not related | XX (XX.X) / XX |
| | Possibly related | XX (XX.X) / XX |
| | Probably related | XX (XX.X) / XX |
| | Definitely related | XX (XX.X) / XX |
| ... | ... | ... |

AE=Adverse Event; MedDRA=Medical Dictionary for Regulatory Activities; TEAE=Treatment-Emergent Adverse Event.

N: the number of subjects in the Safety population.

n: the number of subjects with at least one TEAE within a specific category. Percentages are calculated as $(100 \times n/N)$.

E: total number of TEAEs reported with given category of relationship to study drug.

For 'Overall' and for each SOC and SOC/PT, each subject is counted once in the category of the closest relationship.

For 'Overall', the number of all reported TEAEs are presented; for each SOC and SOC/PT, the number of TEAEs of closest relationship is given.

**MC2-01-C6_STATISTICAL ANALYSIS PLAN_Final 3.0_07 September 2020**
APPENDIX 1 TFLs Shells

If the relationship is missing for a TEAE, then 'Definitely related' category is assigned.
AEs are coded using MedDRA version XX.X.

Path to the program code, date and time of output/ Datasets used/ Referenced Data Listings

Programming note:

System organ classes (SOC) and preferred terms (PT) within each SOC should be sorted in descending order of n (%).

Similar to table 14.3.1.7.1, the following tables will be constructed (with the corresponding corrections of underlined fragments in the note):

Table 14.3.1.7.2 Incidence of Treatment-Emergent Adverse Events up to Week 4 by Closest Relationship

Similar to table 14.3.1.2.1, the following tables will be constructed (with the corresponding corrections of underlined fragments in the note):

Table 14.3.1.8.1 Incidence of Treatment-emergent Adverse Events Leading to Discontinuation of Study Drug
Table 14.3.1.8.2 Incidence of Treatment-emergent Adverse Events Leading to Discontinuation of Study Drug up to Week 4
Table 14.3.1.9.1 Incidence of Treatment-emergent Adverse Events Leading to Withdrawal
Table 14.3.1.9.2 Incidence of Treatment-emergent Adverse Events Leading to Withdrawal up to Week 4
Table 14.3.1.10.1 Incidence of Non-serious treatment-emergent Adverse Events Occurred at a Frequency of >=5%
Table 14.3.1.10.2 Incidence of Non-serious treatment-emergent Adverse Events Occurred at a Frequency of >=5% up to Week 4
Table 14.3.1.11 Incidence of Treatment-emergent Adverse Events Related to Cosyntropin
Table 14.3.1.12 Incidence of Treatment-emergent Adverse Events Related to Study Procedures
Table 14.3.2.1 Incidence of Treatment-emergent Adverse Events Leading to Death
Table 14.3.2.2 Incidence of Treatment-emergent Adverse Events Related to the Study Drug and Leading to Death

MC2-01-C6_STATISTICAL ANALYSIS PLAN_Final 3.0_07 September 2020
APPENDIX 1 TFLs Shells

HPA Axis Suppression

MC2 Therapeutics
MC2-01-C6Table 14.3.4.1.1 Summary of ACTH Challenge Test
HPA population
Page X of X

| Serum Cortisol (nmol/L) | Total (N=XX) | |
|-------------------------|-----------------------|-----------------------|
| | Pre-stimulation | Post-stimulation |
| Baseline | | |
| n | XX | XX |
| Mean [95% CI] | XX.XX [XX.XX - XX.XX] | XX.XX [XX.XX - XX.XX] |
| SD | XX.XX | XX.XX |
| Median | XX.XX | XX.XX |
| Q1, Q3 | XX.XX, XX.XX | XX.XX, XX.XX |
| Min, Max | XX.X, XX.X | XX.X, XX.X |
| Visit 3 / Week 4 | | |
| n | XX | XX |
| Mean [95% CI] | XX.XX [XX.XX - XX.XX] | XX.XX [XX.XX - XX.XX] |
| SD | XX.XX | XX.XX |
| Median | XX.XX | XX.XX |
| Q1, Q3 | XX.XX, XX.XX | XX.XX, XX.XX |
| Min, Max | XX.X, XX.X | XX.X, XX.X |
| Visit 5 / Week 8 | | |
| n | XX | XX |
| Mean [95% CI] | XX.XX [XX.XX - XX.XX] | XX.XX [XX.XX - XX.XX] |
| SD | XX.XX | XX.XX |
| Median | XX.XX | XX.XX |
| Q1, Q3 | XX.XX, XX.XX | XX.XX, XX.XX |
| Min, Max | XX.X, XX.X | XX.X, XX.X |
| Follow-up | | |
| n | XX | XX |
| Mean [95% CI] | XX.XX [XX.XX - XX.XX] | XX.XX [XX.XX - XX.XX] |
| SD | XX.XX | XX.XX |
| Median | XX.XX | XX.XX |
| Q1, Q3 | XX.XX, XX.XX | XX.XX, XX.XX |
| Min, Max | XX.X, XX.X | XX.X, XX.X |

MC2-01-C6_STATISTICAL ANALYSIS PLAN_Final 3.0_07 September 2020
APPENDIX 1 TFLs Shells

HPA=Hypothalamic-pituitary-adrenal.

N: the number of subjects in the HPA population. n: the number of valid measurements.

Measurements of serum cortisol levels pre- and post- stimulation with cosyntropin 0.25 mg are presented.

Path to the program code, date and time of output/ Datasets used/ Referenced Data Listings

**MC2-01-C6_STATISTICAL ANALYSIS PLAN_Final 3.0_07 September 2020**
APPENDIX 1 TFLs ShellsMC2 Therapeutics
MC2-01-C6**Table 14.3.4.1.2 Incidence of HPA Axis Suppression**
HPA population
Page X of X

| | | Total (N = XX) |
|-----------------------------------|-----------------------------------|--------------------------------------|
| HPA axis suppression | | |
| Overall | n' (%) [1] n (%) [2] 95% CI | XX (XX.X) XX (XX.X) XX.X, XX.X |
| Visit 3 / Week 4 | n' (%) [1] n (%) [2] 95% CI | XX (XX.X) XX (XX.X) XX.X, XX.X |
| Visit 5 / Week 8 | n' (%) [1] n (%) [2] 95% CI | XX (XX.X) XX (XX.X) XX.X, XX.X |
| HPA axis suppressed at Week 4 | n' (%) [3] n (%) [2] 95% CI | XX (XX.X) XX (XX.X) XX.X, XX.X |
| HPA axis not suppressed at Week 4 | n' (%) [3] n (%) [2] 95% CI | XX (XX.X) XX (XX.X) XX.X, XX.X |

CI=Confidence Interval; HPA=Hypothalamic-pituitary-adrenal.

N: the number of subjects in the HPA population. n: the number of subjects within a specific category. n': the number of valid observations.

[1] Subjects having any post-baseline values (for 'Overall' category) or values at the corresponding visit. Percentage is calculated as $(100 \times n/N)$.

[2] Percentages are based on the corresponding number of valid observations.

[3] Subjects with corresponding HPA suppression status at Week 4 having values at Visit 5 / Week 8. Percentage is calculated based on number of subjects with corresponding HPA suppression status at Week 4.

Confidence interval is calculated using Clopper-Pearson method.

Adrenal suppression is defined as the 30-minute post-stimulation serum cortisol level below 18 ug/dL (500 nmol/L).

Data MATRIX

SF_STAT001_ver 2_Eng
Approval Date 19 July 2017

MC2-01-C6_STATISTICAL ANALYSIS PLAN_Final 3.0_07 September 2020
